#### **7.7.9 Distribution of Rutherford classification at 30 days and 6 months**

The distribution of Rutherford Classification (RC) will be assessed on the ITT and mITT analysis sets at baseline, 30 days, and 6 months. RC will be summarized by visit using the investigator reported values. The change from baseline, calculated as the follow-up RC value minus the baseline RC value, will be summarized. A negative change indicates improvement.

#### **7.7.10 Change in Ankle Brachial Index after clinical trial treatment compared to baseline**

The change in ABI on the target limb will be assessed on the ITT and mITT analysis sets. The change in ABI after clinical trial treatment compared to the baseline value will be summarized using the investigator reported values. The change will be measured as post-procedure ABI minus baseline ABI. Subjects with a baseline or post-procedure non-compressible vessel (including ABI > 1.4) will be excluded from the calculation as non-compressible vessels cannot be meaningfully interpreted as a continuous variable; these subjects will be presented categorically.

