4. DEFINITIONS

Term	Definition
Acute Device Success	The percentage of patients with the following, post-procedure: 
 a) ≤50% residual stenosis post OAD + POBA [Angiographic Core Lab assessed] and, b) No OAS-related severe angiographic complications defined as severe dissections (D-F), perforation, or distal emboli requiring additional treatment during the procedure [CEC adjudicated]
Acute Procedural Success	Both acute technical success and absence of death, stroke, myocardial infarction (MI), acute onset of limb ischemia, index bypass graft or treated segment thrombosis, and/or need for urgent/emergent vascular surgery within 72 hours of the clinical trial treatment [CEC adjudicated]
Acute Technical success ¹	Achievement of a final residual stenosis <30% for stented and <50% for non-stented subjects by angiography at the end of the procedure [Angiographic Core Lab assessed] without severe angiographic complications defined as severe dissections (D-F), perforation, or distal emboli requiring additional treatment during the procedure [CEC adjudicated]
Adverse Device Effect (ADE)	An adverse event-related to the use of an investigational medical device (per ISO14155:2020) 
Note 1: This definition includes adverse events resulting from insufficient or inadequate instructions for use, deployment,

Term	Definition
	
implantation, installation, or operation, or any malfunction of the investigational medical device.
 
Note 2: This definition includes any event resulting from use error or from intentional misuse of the investigational medical device.
 
Note 3: This includes 'comparator' if the comparator is a medical device.

Adverse Event	Any disease or injury, or its clinical signs occurring in a subject who has been treated with an investigational device or post-marketing study device.
Before Clinical Trial Treatment	Begins when procedural visit window begins. Ends when OAS Guide Wire enters the body.
Clinically-driven target lesion revascularization (TLR)	A repeat procedure performed for $\geq 50\%$ stenosis confirmed by angiography within all or part of the target lesion after documentation of recurrent clinical symptoms of PAD following clinical trial treatment [CEC adjudicated]

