11.4.2 Clinical Trial Treatment Exclusion Criteria

31. Subject has had any Inflow treatment (ipsilateral iliac and/or common femoral artery) that was unsuccessful or had complications prior to OAS guidewire insertion per the following definition:
 - a) $> 50\%$ residual stenosis and/or
 - b) Presence of angiographically assessed dissection (type D-F), perforation, distal embolization, thrombus and/or slow flow/no reflow

32. Target lesion is a chronic total occlusion (CTO) [confirmed by visual estimate via angiography]
33. Subject has presence of any other hemodynamically significant lesions or asymptomatic lesions in the target limb requiring a planned surgical intervention or endovascular procedure 30-days after clinical trial treatment
34. Presence of aneurysm in the target vessel
35. Acute ischemia and/or acute thrombosis of the SFA and/or POP (P1 and/or P2) artery
36. Angiographic evidence of perforation prior to insertion of the CSI Peripheral OAS Guide Wire
37. Angiographic evidence of severe (type D-F) dissection prior to insertion of the CSI Peripheral OAS Guide Wire
38. Planned use of atherectomy (other than CSI Peripheral OAS), laser, other debulking devices, CTO devices, cutting balloons, scoring balloons, specialty balloons or similar devices in the target limb

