11.5 Before Clinical Trial Treatment

- **NON-TARGET LIMB** Non-target limb treatment must occur either greater than 30 days prior to the clinical trial treatment or greater than 30 days after the clinical trial treatment in the study according to **Section 12.4**.
- **INFLOW LESIONS IN THE TARGET LIMB** Inflow lesions (ipsilateral iliac and/or common femoral artery) in the target limb may be treated on the same day as the clinical trial treatment provided.
 - The inflow lesion must be successfully treated defined as residual stenosis \leq 50% without complications prior to insertion of the OAS guidewire in the target lesion to be revascularized. - **Refer to Clinical Trial Treatment Exclusion Criteria 31.**
 - The inflow lesion may only be treated with POBA or stenting.
 - Atherectomy, laser, other debulking devices, CTO devices, cutting balloons, scoring balloons, specialty balloons or similar devices cannot be used for the inflow treatment. - **Refer to Clinical Trial Treatment Exclusion Criteria 38.**
- **NON-INFLOW, NON-TARGET LESIONS IN THE TARGET LIMB**
 - Treatment of lesion(s) not considered Inflow or Target Lesion cannot occur on the day of the clinical trial treatment.
 - Non-target lesion treatment on the target limb must occur greater than 30 days after the clinical trial treatment in the study. - **Refer to General Exclusion Criteria 8 and 10.**
- Access artery by operator's preferred methodology for target limb treatment.

- Cross the lesion using the operator's preferred wire (CSI Peripheral OAS Guide Wire cannot be used at this point).
- Assess Clinical Trial Treatment Inclusion/Exclusion criteria including Calcium Assessment using IVUS and/or angiography – **Refer to Appendix A** to determine when IVUS and angiography images are taken.
 - IVUS Catheter – refer to IVUS IFU to determine appropriate IVUS catheter size.
 - One pass of the IVUS Catheter will be attempted in order to perform Calcium Assessment. If IVUS cannot cross the lesion, do not attempt crossing with IVUS again.
 - Ensure angiographic images have been collected.
 - To complete the Calcium Assessment, **Refer to Appendix B** to determine how to use data from IVUS and/or angiography to determine Calcium Assessment.
- Based on feedback from physician experts, there are no differences in patient characteristics that impact outcomes if calcium is measured by IVUS or angiography.
- Refer to **Figure 1** for the defined treatment area.

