12.4 Non-Target Limb Treatment

If subject presents with bilateral disease with one eligible lesion in both legs, the target limb will be determined by physician's discretion. Non-target limbs requiring PTA treatment must be treated either >30 days prior to clinical trial treatment or > 30 days after clinical trial treatment.

The investigational OAS cannot be used in a non-target limb. The non-target limb should be treated per treating physician's standard of care.

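### The ABI and Rutherford changes absorb any same-day inflow revascularization done before the OAS wire, and the SAP does not show them by inflow status

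*SAP*

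**What the plan says.** **Change formulas.** SAP 7.7.10 takes the target-limb ABI in the ITT and mITT sets: "The change will be measured as post-procedure ABI minus baseline ABI". The only subjects it removes from the calculation are those with non-compressible vessels. SAP 7.7.9 covers Rutherford class in the same sets at 30 days and 6 months: "The change from baseline, calculated as the follow-up RC value minus the baseline RC value, will be summarized".

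**Assessment times.** Protocol 11.1 and Table 7 place baseline ABI and Rutherford at the Baseline visit, up to 30 days before treatment. Table 7 marks neither in the column for the period just before treatment. The next ABI is in the discharge column. The next Rutherford values are at 30 days (required only if that visit is in hospital) and 6 months.

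**Inflow treatment.** Protocol 11.5 states that inflow lesions "in the target limb may be treated on the same day as the clinical trial treatment provided" the inflow result is successful and "without complications prior to insertion of the OAS guidewire in the target lesion to be revascularized". On method: "The inflow lesion may only be treated with POBA or stenting". Clinical Trial Treatment Exclusion 31 (Protocol 11.4.2) removes only inflow treatment "that was unsuccessful or had complications prior to OAS guidewire insertion per the following definition". Subjects with successful inflow treatment stay in.

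**Definitions.** Protocol section 4 defines the phase before Clinical Trial Treatment: "Begins when procedural visit window begins. Ends when OAS Guide Wire enters the body". Clinical Trial Treatment itself starts at that same moment.

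**Later procedures.** Protocol 12.4 lets the other limb be treated "> 30 days after clinical trial treatment". Protocol 11.5 sets the same 30-day limit for other lesions in the target limb.

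**The concern.** The endpoint is named as a change after clinical trial treatment, but the interval it spans can contain a second revascularization of the same limb that the protocol places outside that treatment. Relieving a proximal stenosis would be expected to raise ankle pressure and ease claudication without any help from the study device. There is no control arm in which the same co-intervention would cancel out.

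At stake is how two descriptive secondary endpoints are read in a study meant to support commercialization. ABI and Rutherford are among the few endpoints that describe haemodynamic or symptomatic benefit after the procedure. As the plan stands, a reader of the report could not tell how much of either change came from subjects whose inflow was also opened.

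**Working it through.** **1. Is there a plan figure to reproduce?** Not for this point. The documents give no expected ABI or Rutherford change, no inflow frequency and no inflow effect. The only sample-size figure is for Acute Device Success, and it reproduces: [(1.96 × √(0.5 × 0.5) + 1.2816 × √(0.7 × 0.3)) / 0.2]² = 61.41, rounded up to 62. Nothing below enters that calculation.

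**2. Order of events for a subject with inflow disease**

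| Step | Event | Source |
|---|---|---|
| 1 | Baseline ABI and Rutherford, up to 30 days before | Protocol 11.1, Table 7 |
| 2 | Inflow balloon or stent, same day | Protocol 11.5 |
| 3 | OAS guide wire enters; Clinical Trial Treatment starts | Protocol section 4 |
| 4 | OAD, POBA, DCB | Protocol 12.2 |
| 5 | ABI before discharge | Table 7 |
| 6 | Rutherford at 30 days and 6 months | Table 7 |

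The ABI change is step 5 minus step 1, and the Rutherford change is step 6 minus step 1. Both contain step 2. That step 2 follows step 1 is inferred from Table 7 and Protocol 11.5 together; no single sentence says so.

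**3. Does anything visible separate these subjects?** SAP 7.7.9 and 7.7.10 are readable and contain no such rule. The covariate analysis in SAP 7.8 concerns Acute Device Success only, and its visible covariates (gender, calcium, lesion length, renal disease) do not include inflow treatment.

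**4. Size for ABI.** Let s be the share with same-day inflow treatment and g the mean ABI gain due to it.

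Inflation of the mean change = s × g.

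Both inputs are assumptions:

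| s | g = 0.05 | g = 0.10 | g = 0.20 | g = 0.30 |
|---|---|---|---|---|
| 5% | 0.003 | 0.005 | 0.010 | 0.015 |
| 10% | 0.005 | 0.010 | 0.020 | 0.030 |
| 20% | 0.010 | 0.020 | 0.040 | 0.060 |
| 30% | 0.015 | 0.030 | 0.060 | 0.090 |

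The first cell is 0.0025 before rounding. Of 62 subjects, 5% is 3.1 and 30% is 18.6, so about 3 to 19 people.

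**5. Size for Rutherford.** If a share s improves one class because of inflow treatment, the mean change shifts by s × 1 towards improvement. For s = 10% that is 0.1 class.

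**6. Precision of a no-inflow row.** With equal variance, its standard error is 1/√(1 − s) times that of the full set: 1/√0.95 = 1.03 at 5%, and 1/√0.70 = 1.20 at 30%. At 30%, 62 × 0.70 = about 43 subjects remain.

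**The case against.** **No decision rests on these endpoints.** Protocol 25.4.3 attaches no hypothesis test to any secondary endpoint, and success depends only on Acute Device Success. This stands, and it limits the weight of the point.

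**The change was never that of the OAS alone.** The regimen is OAD, POBA and DCB, with stents possible. True, but those belong to the defined treatment or follow it. Inflow balloon or stent treatment comes before it.

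**Other co-interventions are already controlled.** Protocol 11.5 bars same-day treatment of other target-limb lesions, 12.4 bars other-limb treatment within 30 days either side, and Exclusions 10 and 33 bar planned procedures in the 30 days after. This stands: the discharge ABI is exposed essentially to inflow treatment only, and the 30-day Rutherford largely so.

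**Repeat procedures are visible elsewhere.** Clinically driven TLR counts as failure in patency (SAP 7.7.4) and in MAE (SAP 7.7.7). That is correct, but it does not label a Rutherford value obtained after such a procedure.

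**A rule may sit in blacked-out text.** The ITT and mITT definitions and parts of SAP sections 6 and 7.8 cannot be read. A general rule there cannot be excluded.

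**Stronger readings a reader might infer.** One is that later procedures also bias the 6-month Rutherford in the device's favour. The documents do not establish that: a later procedure may follow worsening, and untreated disease in the other limb can mask benefit. Another is that the main summary should be limited to subjects with no further target-limb revascularization. That would remove clinical failures such as TLR, selecting on an outcome and tending to flatter the device. A third is that the distortion differs by site; the documents give no inflow rates by site.

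**Conclusion.** The point holds for same-day inflow treatment. As written, the ABI and Rutherford changes include its effect, in the device's favour for the subjects who receive it, and no readable rule separates them. The illustrative inflation of about 0.003 to 0.09 ABI units rests wholly on the assumed shares and gains. It is negligible at the low end and worth seeing at the high end, and the documents do not cap the share. It would be wrong to infer that the trial's main conclusion is affected: the primary test and N = 62 do not use either measure. This is a low-cost improvement to the reporting of descriptive endpoints.

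**What to change.** In SAP 7.7.10 and 7.7.9:

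1. Keep the all-subject ITT and mITT summaries as they are.
2. Add rows for subjects without and with same-day inflow treatment, for ABI change and for 30-day and 6-month Rutherford change.
3. State that any comment on the effect of the trial treatment rests on the no-inflow row. That row still describes the combined regimen, not the OAS alone.
4. For 6-month Rutherford, do not exclude subjects revascularized again before the visit, whether at the target lesion or elsewhere. Keep them in the denominator and show them in a separate row, so that a value obtained after a repeat target-lesion procedure is not presented as improvement from the trial treatment.

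**Cost.** SAP wording and a few table rows, with no change to eligibility, treatment or sample size. The subgroup rows will be small. The forms are not among the documents, so a dated flag for inflow treatment and for later revascularization must be confirmed. Later procedures need particular attention: under Protocol 14, contacts between visits are not recorded on a form unless an adverse event is noted, and under 16.2 a planned admission for a pre-existing condition, without serious deterioration in health, is not a serious event. A planned procedure elsewhere could therefore go unrecorded.

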## 7.8 Covariate Analyses

An analysis will be performed to assess covariates that may introduce a confounding effect for the primary endpoint of Acute Device Success. The analysis will be performed using logistic regression on the mITT population. Univariable analysis will be performed on the following covariates:

- Gender
- Moderate or severe calcium per PARC definition (per IPR assessment)
- Lesion length
- Renal Disease

[REDACTED]

[REDACTED]

[REDACTED]

[REDACTED]

## 7.9 Pooling Data Across Investigational Sites

The appropriateness of pooling data across sites will be assessed on the mITT analysis set. The primary endpoint will be presented separately for each investigational site using descriptive statistics.

[REDACTED]

[REDACTED]

[REDACTED]

[REDACTED]

[REDACTED]

[REDACTED]

[REDACTED]

[REDACTED]

## 8 OTHER ANALYSES

[figure not shown]
No further analyses are planned outside those outlined in **Section** Error! Reference source not found. Error! Reference source not found.. Unless specifically requested, any ad hoc analyses, including those requested by the Pharmaceutical and Medical Devices Agency (PMDA), will follow the guidelines outlined in this document. Deviations from the SAP will be outlined in a dedicated section of any report.

## 9 VERSION CONTROL

[REDACTED]	[REDACTED]	[REDACTED]
[REDACTED]	[REDACTED]	[REDACTED]
[REDACTED]	[REDACTED]	[REDACTED]

■		
■		

A bar chart consisting of 20 horizontal bars of varying lengths, arranged in a descending order from left to right. The bars are black on a white background. The first bar is located at the bottom left, and the last bar is located at the top right. The bars are of different widths, representing different data values.

